6.1.2. Assessment of Safety

Evidence in Kidney Injury

Serum creatinine will be obtained just before administration and at the end of the 6 hour observation period.

Adverse Events

Incidence of Treatment-Emergent adverse events (AEs) or serious adverse events (SAEs) will be assessed. Treatment associated pain and any local skin reaction including hematoma, induration, infection, thrombosis, necrosis etc. will be assessed.

6.1.3. Clinical Laboratory Tests

All routine samples will be analyzed by a licensed clinical laboratory. The clinical laboratory tests are as follows:

- **Blood Clinical Chemistry**: blood urea nitrogen (BUN), creatinine, sodium, potassium, calcium, chloride, magnesium and bicarbonate.
- BNP/NTproBNP
- Urinalysis: A 5 ml aliquot from the first void post start of treatment and a 5 ml aliquot from the pooled urine voids over the 6 hour observation period will be analyzed for sodium.

6.1.4. Physical Examinations

A cardiopulmonary examination will be conducted and consist of assessments of the following: heart sounds, murmur, chest sounds, pedal edema and peripheral pulses.

6.1.5. Heart Failure Symptom Scoring

The Kansas City Cardiomyopathy questionnaire will be used in this study to assess subjects and monitor overall response to treatment.

6.1.6. Vital Signs

Vital signs will include respiration rate (breaths per minute), oral temperature, and supine blood pressure (mmHg) and heart rate (beats per minute [bpm]). Blood pressure and heart rate will be obtained after the subject has been resting in supine position for 5 minutes.

6.1.7. 12-Lead ECG

12-lead ECGs will be performed after the subject has rested quietly for at least 5 minutes in a supine position.

6.1.8. Pain Assessment

Pain assessment will be conducted at the end of the 6 hour observation period. Subjects will be asked to verbally rate the intensity of any discomfort using numeric rating scale of 0 to 10 with zero equivalent to no pain and 10 being the worst possible pain. (Appendix 2)

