| ENDPOINTS | Primary Endpoints: |
| | Total volume of voids over a 6-hour period Total natriuresis over a 6-hour period |
| | Secondary endpoints: |
| | Volume of voids between 0-2 hours, 2-4 hours and 4-6 hours post initiation of treatment. Heart Failure Symptom Scoring/Symptom Improvement- (Kansas City Cardiomyopathy questionnaire) Overall Satisfaction with Treatment- (Treatment Satisfaction |
| | Survey) |
| | Safety endpoints: |
| | Patient reported Pain Increases in serum creatinine of 0.5 mg/dL or greater Local skin reactions including hematoma, induration, infection, thrombosis, necrosis etc. Occurrence of treatment-emergent Adverse Events (AEs) or Serious Adverse Events (SAEs) |
| STATISTICAL ANALYSIS | Determination of Sample Size: For this pilot study, the determination of sample size was primarily based on clinical consideration; with the aim to yield meaningful preliminary data. |
| | Statistical Analysis Plan: A full statistical analysis plan will be developed. All data will be analyzed as intention-to-treat. Continuous variables will be presented as mean \pm standard deviation and will be compared using the Students t -test (2-tailed), unpaired. Differences between treatment groups for the categorical variables will be analyzed using the chi-square test. For the purposes of this study, P values \leq .05 will be considered significant. |
| | Early Stopping Rules: The study will be stopped early if there is a significant difference in number of patients with intolerable side effects: Ototoxicity, severe discomfort, burning and stinging at the access site, itching, and/or pain. |

| Time and Events Table | Screening Phase | Pre-Dose | Start of Dosing | Dosing | 6 hours post Start of Dosing |
|---|--------------------|----------|--------------------|--------|---------------------------------|
| Informed Consent | Х | | | | |
| Confirmation of Eligibility | Х | | | | |
| Co-morbidity | Х | | | | |
| Cardio-Pulmonary Examination | Х | | | | |
| Serum Creatinine | Х | | | | Х |
| Weight and Height | Х | | | | |
| Vital Signs | Х | Х | Х | Х | Х |
| 12-lead EKG | Х | | | | |
| Collection and Measurement of Urine Voids | | | Х | Х | Х |
| Urine Sodium | | Х | | | Х |
| Clinical Chemistry | Х | | | | Х |
| BNP/NT ProBNP | | Х | | | Х |
| Study Drug Administration | | | Х | | Х |
| Injection Site Pain Assessment | | | | | Х |
| Injection Site Inspection | | Х | | | Х |

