1.1. Rationale for the Current Study

The research hypothesis is that subcutaneously administered furosemide will be an effective alternative to IV furosemide for hemodynamically stable chronic heart failure patients presenting with volume overload in the ambulatory setting. The significance of this research is finding a potential intervention that could help decrease heart failure hospitalizations and improve the quality of life for patients with chronic heart failure. In addition, we can decrease the costs associated with heart failure.

There is very little experience with subcutaneous administration of furosemide EP/USP (current form of commercially available furosemide injection solution). There are a few studies that show the delivery of subcutaneous furosemide by electric infusion pump in terminally ill patients is effective for weight loss and symptom improvement (1,2). A group in Spain was successfully able to resolve 41 episodes of decompensated heart failure in 24 elderly patients using continuous subcutaneous furosemide administered by elastomeric infusion pumps (2). They found that the elastomeric infusion pumps provided safe outpatient treatment without the need for daily monitoring. In addition, it helped prevent hospital admissions and decreased costs due to the low price of the devices. It was also a good alternative for patients with venipuncture failure and the inability to transition from intravenous to oral diuretics.

Furosemide USP has a pH of 8.3 -9.0 and may cause irritation and discomfort upon administration. A novel buffered formulation with a physiologic pH (7.4) is currently under development in support of a NDA submission later in 2015. The product is to be marketed with a wearable patch pump for a slow 5-hour administration to optimize 8-hour diuresis.

scPharmaceuticals, Inc. (Lexington, MA), the developer of the novel furosemide formulation and its drug delivery device, provided the following information. The pivotal clinical study with the buffered furosemide solution (Furosemide Injection Solution (SCP-101)) started in Q2 of 2015 in support of the NDA. This study is conducted in the United States in stable HF patients under IND 118,919.

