2. STUDY OBJECTIVES

The objectives of this study are:

(1) Primary objective: To determine the clinical efficacy of subcutaneously administered Furosemide Injection Solution (SCP-101) versus intravenous administration of Furosemide Injection, USP in adult patients at the HFBC presenting with decompensated heart failure.

(2) Secondary objective: To determine the adverse effects and patient satisfaction with subcutaneously administered SCP-101 versus intravenous furosemide in adult patients at the HFBC presenting with decompensated heart failure.

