- *Furosemide Injection Solution, 8 mg/mL (SCP-101):* 80 mg dose administered subcutaneously as 30 mg over the first hour and then as 12.5 mg per hour over the subsequent 4 hours (test treatment)

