3.1.2. Safety Endpoints

- 1) Patient reported Pain
- 2) Increases in serum creatinine of 0.5 mg/dL or greater
- 3) Local skin reactions including hematoma, induration, infection, thrombosis, necrosis etc.
- 4) Occurrence of treatment-emergent Adverse Events (AEs) or Serious Adverse Events (SAEs)

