Appendix 1: Time and Events Schedule

| Time and Events Table | Screening Phase | Pre-Dose | Start of Dosing | Dosing | 6 hours post Start of Dosing |
|---|--------------------|----------|--------------------|--------|---------------------------------|
| Informed Consent | Х | | | | |
| Confirmation of Eligibility | Х | | | | |
| Co-morbidity | Х | | | | |
| Cardio-Pulmonary Examination | Х | | | | |
| Serum Creatinine | Х | | | | Х |
| Weight and Height | Х | | | | |
| Vital Signs | Х | Х | Х | Х | Х |
| 12-lead EKG | Х | | | | |
| Collection and Measurement of Urine Voids | | | Х | Х | Х |
| Urine Sodium | | Х | | | Х |
| Clinical Chemistry | Х | | | | Х |
| BNP/NT ProBNP | | Х | | | Х |
| Study Drug Administration | | | Х | | Х |
| Injection Site Pain Assessment | | | | | Х |
| Injection Site Inspection | | Х | | | Х |
| Randomization to Treatment Sequence | Х | | | | |
| Kansas City Cardiomyopathy questionnaire | | Х | | | Х |
| Treatment Satisfaction Survey | | | | | Х |
| Treatment Emergent Serious Adverse Events | | | X | X | Х |

Verbally indicate the number on the Numeric Rating Scale that best represents the intensity of pain at or around the injection site NOW, with 0 being no pain and 10 being the worst possible pain.

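### The only scheduled 0–10 pain score asks at 6 hours about pain now, so it misses pain during either administration, and section 6.1.8 words the question differently from the scale

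*Combined protocol and SAP*

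**What the plan says.** The first safety endpoint in section 3.1.2 is "Patient reported Pain". The procedure is in section 6.1.8: "Pain assessment will be conducted at the end of the 6 hour observation period". The time and events tables in the synopsis and in Appendix 1 agree with this. The row "Injection Site Pain Assessment" has a single mark, in the column for 6 hours after the start of dosing, and none before or during dosing.

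The question itself is worded in two ways:

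- Section 6.1.8: "Subjects will be asked to verbally rate the intensity of any discomfort using numeric rating scale of 0 to 10".
- The scale text, printed between Appendix 1 and Appendix 3: "intensity of pain at or around the injection site NOW".

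The test treatment is described in section 3.1 as "80 mg dose administered subcutaneously as 30 mg over the first hour and then as 12.5 mg per hour over the subsequent 4 hours". Section 5.4 has the IV dose given as a single bolus lasting about 2 minutes. Section 8.3 has pain tabulated and described, with no formal test.

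**The concern.** The secondary objective in section 2 is "To determine the adverse effects and patient satisfaction with subcutaneously administered SCP-101 versus intravenous furosemide". How painful each administration was is part of that comparison. Section 1.1 introduces the buffered product after noting that furosemide USP "may cause irritation and discomfort upon administration". A score that asks only about the present moment, taken after both administrations have finished, cannot show how uncomfortable either one was. Low scores in both arms at 6 hours could be misread as showing that both routes were comfortable, when pain during dosing may simply have resolved.

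The difference in wording adds a second problem. If section 6.1.8 is followed without the scale text, subjects may choose their own time frame and body site, and scores may not mean the same thing from one subject to the next.

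**Working it through.** **Inputs**

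- Subcutaneous regimen: 30 mg in the first hour, then 12.5 mg/h for 4 hours (sections 3.1 and 5.4).
- IV bolus: about 2 minutes (section 5.4).
- Pain score: once, 6 hours (360 minutes) after the start of dosing (section 6.1.8 and both time and events tables).

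**The plan's own figures.** Dose = 30 × 1 + 12.5 × 4 = 80 mg. Duration = 1 + 4 = 5 h = 300 min. Both match the protocol.

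**Time from end of delivery to the score** = 360 min minus the end of delivery.

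- Subcutaneous: 360 − 300 = 60 min.
- IV: 360 − 2 = 358 min. If about 2 minutes is taken, as an assumption, to mean 1 to 5 minutes, the range is 359 to 355 min.
- Difference between arms: 358 − 60 = 298 min; ratio 358/60 ≈ 6.

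**Coverage under the current-pain wording.** The score covers 0 of the 300 minutes of subcutaneous delivery, which is 300/360 = 83% of the observation period, and 0 of the roughly 2 minutes of the bolus.

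**Coverage of a worst-since-dosing question at 360 min.** It would cover 360 of 360 minutes in both arms. For pain felt during delivery, the recall interval would be:

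- Subcutaneous (delivery from 0 to 300 min): 60 to 360 min.
- IV (delivery from 0 to 2 min): 358 to 360 min.

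**The two wordings side by side**

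| | Section 6.1.8 | Scale text |
|---|---|---|
| Symptom | any discomfort | pain |
| Site | none named | at or around the injection site |
| Time frame | none stated | now |

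**Other routes by which pain during dosing could be recorded**

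- Side-effect monitoring of the access site (synopsis and section 3.1): no instrument or time points given.
- Assessment of treatment-associated pain (section 6.1.2): no scale given.
- Adverse events: assessed continuously until discharge (section 7), asked about with an open question at 6 hours (section 7.5), graded mild, moderate or severe by the investigator or designee (section 7.3) and documented on the CRF (section 7.6.4).
- The early stopping rule (synopsis and section 4.4): relies on the number of patients with intolerable side effects, including access-site symptoms.
- The Treatment Satisfaction Survey at 6 hours (section 6.1.1): content not given, so whether it asks about discomfort during treatment is unknown.

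None of the first four includes a 0–10 patient rating.

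**The case against.** The strongest reply is that little is lost. Section 6.1.8 refers staff to Appendix 2 and uses the same end points of 0 and 10 as the scale, and the time and events tables name the injection site. The section can therefore be read as a summary of the scale rather than a rival to it. Pain during dosing has several other routes into the record, and the endpoint is not stated to rest on the 0–10 score alone. Residual pain at 6 hours is a legitimate measure. The remark in section 1.1 concerns furosemide USP, and no arm receives unbuffered furosemide subcutaneously, so no pain score here could test that rationale directly. This is a 40-patient pilot in which pain is only described.

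Much of this stands. It makes the wording mismatch secondary, although *any discomfort* and *pain at the site now* remain different questions. It also means that pain during dosing is not lost altogether. But the other known routes provide a count or an investigator's grade in an open-label study, not a patient's rating. The comparison of adverse effects is a stated objective whatever weight section 1.1 is given.

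Two caveats also stand. Both time and events tables mark study drug administration at 6 hours and not in the dosing column, which does not fit the 5-hour infusion in the text; these places must be reconciled. Even if delivery ran to 6 hours, a current-pain score would miss almost all of the infusion and all of the bolus. In addition, no Appendix 2 heading appears in the text as read, so the scale page may not be complete.

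**Conclusion.** The concern holds. As written, the one scheduled patient-rated pain score can support a statement about pain remaining at 6 hours: 60 minutes after subcutaneous delivery ends and about 358 minutes after the bolus. It cannot support a statement about how painful either administration was.

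This rests on the scale text being what subjects are asked, and on the infusion running for 5 hours without interruption. The gaps are times since drug delivery; removal times for the IV and subcutaneous access are not stated. No sample size, power figure or formal test is affected. The documents give no basis for saying which arm would be favoured. The change should be made because it determines what the trial can say about tolerability and costs little.

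**What to change.** At the existing 6-hour assessment, in both arms, add a 0–10 rating of *worst pain or discomfort at the injection or access site since dosing started*. Report it as the measure of administration pain, alongside the current-pain score, which is kept. Reword section 6.1.8 and the scale so that, for each of the two ratings, both state the same symptom, site and recall period.

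The cost is one extra question, a revised scale page and one CRF field, with no extra visit or time point. The drawback is some recall error, and it is unequal between arms: pain from the bolus must be recalled over about 358 to 360 minutes, whereas pain late in the infusion may be as recent as 60 minutes. The report should say so.

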6.1.9. Injection Site Inspection

Study staff will inspect the injection site for erythema and edema using the Draize Scale which includes a 5-point scale for erythema and a 5-point scale for edema. (Appendix 3)

In addition to the Draize scale scoring, the investigator will assess the injection site area for other local reactions, including hematomas, thrombosis, induration, infection, necrosis, etc. The Investigator will rate the reactions as mild, moderate or severe and make an assessment as to causality.

6.1.10. Meals and Dietary Restrictions

Participants will not be given any fluid by mouth during the 6-hour observation period, except when required for taking oral medication, in which case fluid intake will be limited to 100mL over the 6 hour observation period.

7. ADVERSE EVENTS

The Investigator is responsible for the detection and documentation of events meeting the definition of an AE or SAE as provided in this protocol. Only treatment-emergent AEs and SAEs (occurring after the first dose of study drug through the appropriate follow-up period) will be recorded in this study. Treatment Emergent AEs, will be assessed continuously after administration of study drug through discharge.

7.1. Definition of an Adverse Event

An AE is any untoward medical occurrence in a patient or clinical investigation subject administered a pharmaceutical product which does not necessarily have a causal relationship with this treatment.

An AE can therefore be any unfavorable and unintended sign (that could include a clinically significant abnormal laboratory finding), symptom, or disease temporally associated with the use of a medicinal product, whether or not considered related to the medicinal product.

An AE **does** include any:

- Exacerbation of a pre-existing illness.
- Increase in frequency or intensity of a pre-existing episodic event or condition.

- Condition detected or diagnosed after study drug administration even though it may have been present prior to the start of the study.
- Continuous persistent disease or symptoms present at baseline that worsen following the start of the study.

An AE **does not** include a/an:

- Medical or surgical procedure (e.g., surgery, endoscopy, tooth extraction, transfusion); the condition that leads to the procedure is an AE.
- Pre-existing diseases or conditions present or detected at the start of the study that do not worsen.
- Situations where an untoward medical occurrence has not occurred (e.g., hospitalization for cosmetic elective surgery, social and/or convenience admissions).
- Overdose of either study drug or concurrent medication without any signs or symptoms.
- Hospitalization for elective treatment of a pre-existing condition that did not worsen during the study is not considered an AE.

7.2. Definition of a Serious Adverse Event

An SAE is any AE occurring at any dose that results in any of the following outcomes:

- a. Death.
- b. A life-threatening AE.
 - NOTE: Life-threatening means that the subject was, in the view of the Investigator, at immediate risk of death from the event as it occurred. This definition does not include an event that, had it occurred in a more severe form, might have caused death.
- c. Inpatient hospitalization or prolongation of existing hospitalization.
 - *NOTE:* Complications that occur during hospitalization are AEs. If a complication prolongs hospitalization, the event is an SAE.
 - NOTE: "Inpatient" hospitalization means the subject has been formally admitted to a hospital for medical reasons. This may or may not be overnight. It does not include presentation at a casualty or emergency room.
- d. A disability/incapacity.
 - NOTE: The term disability means a substantial disruption of a person's ability to conduct normal life functions. This definition is not intended to include experiences of relatively minor medical significance such as uncomplicated headache, nausea, vomiting, diarrhea, influenza, accidental trauma (i.e., sprained ankle) that may interfere or prevent everyday life functions but do not constitute a substantial disruption.
- e. A congenital anomaly in the offspring of a subject who received drug.

- f. Important medical events that may not result in death, be life-threatening, or require hospitalization may be considered an SAE when, based upon appropriate medical judgment, they may jeopardize the subject and may require medical or surgical intervention to prevent one of the outcomes listed in this definition. Examples of such medical events include allergic bronchospasm requiring intensive treatment in an emergency room or at home, blood dyscrasias or convulsions that do not result in subject hospitalization, or the development of drug dependency or drug abuse.
 - Medical and scientific judgment should be used in deciding whether prompt reporting is appropriate in this situation.

7.3. Severity of AEs/SAEs

The severity (mild, moderate, or severe) of each AE/SAE must be assessed by the Investigator or designee. The following criteria should be considered when assessing severity:

- Mild The symptom is barely noticeable to the subject and does not influence performance or functioning.
- Moderate The symptom is of sufficient severity to make the subject uncomfortable, and performance of daily activities is influenced. Treatment for the symptom may be needed.
- Severe The symptom causes severe discomfort. Treatment for the symptom may be necessary.

7.4. Assessment of Relatedness to Study Drug

The Investigator will assess each AE and SAE for causality based on their medical judgment and the observed symptoms associated with the event. Each AE and SAE will be assessed as related or unrelated to study drug based on the following criteria:

- Unrelated This category applies to those AEs that the Investigator determines are most likely due to extraneous causes (disease, environment, etc.)
- Related This category applies to those AEs that the Investigator determines are most likely due to test drug.

7.5. Method, Frequency, and Time Period for Detecting Adverse Events and Serious Adverse Events

Patients will be evaluated for AEs and SAEs at the end of the 6 hour observation. After the subject has had an opportunity to spontaneously mention any problems, the Investigator should inquire about AEs by asking a non-leading question such as "How are you feeling?"

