3. INVESTIGATIONAL PLAN

3.1. Overall Study Design and Plan

This clinical trial is a prospective, randomized, parallel-group pilot study comparing the intravenous administration of Furosemide Injection, USP, to subcutaneous administration of a buffered furosemide formulation – Furosemide Injection Solution (SCP-101), in patients presenting to the Johns Hopkins Hospital Heart Failure Bridge Clinic with decompensated heart failure. Patients presenting to the HFBC will be assessed to determine whether they need IV diuretics. If they need it, they will be screened for eligibility. If they are eligible, written informed consent will be provided. Patients will then be randomized to receive Furosemide Injection, USP intravenously, or SCP-101 delivered subcutaneously. The IV patients will get the usual care of the Heart Failure Bridge Clinic, which includes having an IV placed and delivery of a one-time dose of IV furosemide with the dose determined by the providers (maximum dose 160mg IV). The subcutaneous patients will receive 80mg of Furosemide Injection Solution, 8 mg/mL, administered subcutaneously over 5 hours (30mg in first hour and 12.5mg/hour for 4 hours).

Administration will take place with the BBraun Perfusor® Space Infusion Pump System and a standard commercial infusion set. Both groups of patients will be observed for 6 hours to assess diuresis. The goal will be to enroll a total of 40 patients, 20 in the IV furosemide group, and another 20 in the subcutaneous furosemide group. Vital signs and urine output

will be monitored closely for 6 hours. Patients will be asked to fill out a survey about their symptom improvement (Kansas City Cardiomyopathy questionnaire) and overall satisfaction related to the treatment experience. They will also be monitored for side effects including ototoxicity and discomfort at the access site (burning, itching, and pain). Electrolytes and renal function will be checked once after the patients receive diuretic therapy. Study participants will be on fluid restriction during the study, with no more than 100 ml of fluid consumed during the 6 hours.

Study Drug:

- *Furosemide Injection, USP:* Furosemide Injection, Solution, single dose determined by Investigator (maximum dose 160mg) administered intravenously by IV bolus over approximately 2 minutes (reference treatment).

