5.2. Identity of Investigational Product(s)

Furosemide Injection Solution, 8mg/mL (SCP-101): 80 mg undiluted buffered furosemide solution, manufactured by Cook Pharmica, Bloomington, IN, USA for scPharmaceuticals, Inc. under GMP conditions (test treatment).

Contains Tris Hydrochloride, Sodium Chloride and may contain Sodium Hydroxide and Hydrochloric acid for pH adjustment: pH 7.4 (7.0 - 7.8). Furosemide Injection Solution (SCP-101) will be provided by scPharmaceuticals to the investigational site.

Furosemide Injection, USP: Furosemide Injection, Solution, single dose determined by Investigator (maximum dose 160mg) by intravenous bolus administration. (reference treatment)

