5.2.1. Labeling

Study test drug (Furosemide Injection Solution (SCP-101)) will bear a label that meets applicable laws for an investigational drug, which may include, but is not limited to, the following information:

- Federal law statement
- Batch number
- Storage information

Furosemide Injection, USP for intravenous administration will be obtained from local pharmacy commercial stock with commercial labeling.

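### Section 7.4 contradicts itself on causality: it assesses relatedness to study drug (both arms), but defines Related by the test drug, a label the protocol gives only to SCP-101.

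*Combined protocol and SAP*

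**What the plan says.** The heading of section 7.4 refers to study drug, and so does its lead-in: "Each AE and SAE will be assessed as related or unrelated to study drug based on the following criteria". Two categories follow. One is "Related This category applies to those AEs that the Investigator determines are most likely due to test drug". The other is "Unrelated This category applies to those AEs that the Investigator determines are most likely due to extraneous causes (disease, environment, etc".

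Section 3.1 (and the synopsis) lists two products under the heading Study Drug. Intravenous furosemide is "administered intravenously by IV bolus over approximately 2 minutes (reference treatment"). SCP-101 is given subcutaneously, ending with "12.5 mg per hour over the subsequent 4 hours (test treatment"). Section 5.2 repeats the test and reference labels. The labelling section, 5.2.1, begins "Study test drug (Furosemide Injection Solution (SCP-101)) will bear a label".

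Section 6.1.9 separately asks the investigator to judge the causality of local reactions at the injection site. It gives no categories and does not refer to section 7.4. Section 7.6.2 makes the relationship to study drug a required item in every serious adverse event report.

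**The concern.** The secondary objective is to compare adverse effects between subcutaneous and intravenous treatment. Attribution is comparable only if the same question is asked in both arms. Here the section announces one question (was it the study drug?) and supplies the criterion for another (was it the test drug?). An investigator who follows the criterion asks something that, in the intravenous arm, can only be answered no. An investigator who follows the lead-in asks the same question in both arms. The trial is open label (section 5.5), so the arm is known whenever the rule is applied.

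The second gap concerns the route. The arms differ in access and delivery as well as in formulation: an IV line and bolus in one, a pump and commercial infusion set in the other. Section 3.1.2 lists hematoma, infection and thrombosis among the local reactions that are safety endpoints, and these can arise from access as well as from drug. Section 7.4 does not say how to classify an event caused by the access or the procedure.

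**Working it through.** No arithmetic beyond a head count applies. The check is how the terms are used.

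1. **Study drug.** Section 3.1 and the synopsis list SCP-101 and Furosemide Injection, USP under this heading. The term therefore covers both arms.

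2. **Test.** As a treatment label it is attached only to SCP-101: *test treatment* in the synopsis, section 3.1 and section 5.2; *study test drug* in section 5.2.1; *test product* in section 9.1.9. The exact words *test drug* occur only in sections 5.2.1 and 7.4, and section 5.2.1 identifies the product by name.

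3. **Reference.** Intravenous furosemide is the reference treatment in the synopsis, section 3.1 and section 5.2. It is nowhere called test.

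4. **Section 7.4 under each reading.** Planned enrolment is 20 intravenous and 20 subcutaneous, 40 in all (section 3.1).

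| Reading of Related | Patients who could contribute a Related event |
|---|---|
| Criterion as written (test drug = SCP-101) | 20 of 40, subcutaneous arm only |
| Lead-in and heading (study drug = both products) | 20 + 20 = 40 of 40 |

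Under the first reading, 40 − 20 = 20 patients, half the trial, are excluded from Related by definition.

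5. **Access and procedure.** An event caused by a needle, line, infusion set or pump is not caused by a drug, so it fails the Related criterion. Unrelated requires an extraneous cause, with disease and environment as examples in an open list. Whether the study's own delivery equipment is extraneous is not stated, so the category is undefined. Section 6.1.9 does not fill the gap, because its causality assessment has no stated scale.

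6. **Where relatedness is used.**
   - Section 7.4: recorded for each event.
   - Section 7.6.2: a required field in serious adverse event reports.
   - Section 3.1.2: the endpoint is occurrence of events, with no relatedness condition.
   - Section 8.3: adverse events are summarised descriptively, and pain and site reactions are tabulated; neither is split by relatedness.
   - Section 7.6.1: the reporting times have no relatedness filter, and death or a life-threatening event is notified whatever its cause.
   - Section 4.4: the stopping rule refers to intolerable side effects and does not mention relatedness.

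**The case against.** The strongest reply is that this is a drafting slip. The heading, the lead-in and the report field in section 7.6.2 all say study drug, and a sensible investigator would read the criterion that way. The SC-versus-IV comparison can also be made in full from all events regardless of cause.

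Much of that stands, and it rules out several stronger readings.

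- **That the protocol has settled that no intravenous-arm event can be related.** It has not. The lead-in says the opposite of the literal criterion, so this is a contradiction to reconcile, not an established exclusion.
- **That access or pump harms are classed as unrelated.** Nothing says so. A two-category scale may push them there by default, but section 7.4 leaves the question open and section 6.1.9 requires its own causality judgement for site reactions.
- **That the planned safety comparison will show a spurious difference.** No table or test of related events is planned.
- **That the threshold of most likely must be relaxed.** That is a debatable design choice, and curing the contradiction does not require it.

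What does not stand is leaving the wording alone because the intent can be guessed. The criterion is the operative sentence, and its wording matches the protocol's own label for one arm.

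**Conclusion.** The contradiction is real and lies in an operative rule. Depending on which sentence is followed, either 20 or all 40 planned patients can have a Related event. Relatedness as recorded, and the relationship field in serious adverse event reports, would then not be comparable between arms. Events caused by access or delivery have no defined category, and the site-reaction assessment is not linked to the scale.

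The consequence is limited: occurrence of events, pain and local reactions is captured whatever the attribution, and no stated endpoint, test or stopping rule turns on it. This rests on two things: that *test* in section 7.4 means what it means elsewhere in the protocol, and that the full statistical analysis plan promised in section 8.2 adds no analysis by relatedness. If it did, the defect would carry into that analysis. The wording should be corrected; it does not threaten the primary comparison.

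**What to change.** Three edits, made before any attribution is recorded, because judgements made under two readings cannot reliably be repaired afterwards.

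- In the Related criterion of section 7.4, replace *test drug* with *study drug (SCP-101 or Furosemide Injection, USP, as assigned)*.
- Add a sub-category for attribution to the access or administration procedure (IV line, needle, infusion set, pump), recorded identically in both arms.
- In section 6.1.9, state that the causality of site reactions is assessed on the section 7.4 scale.

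The cost is one paragraph and one box on the case report form. The count of related events may be slightly higher, mainly in the intravenous arm.
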